8.4 Visit 3 (Week 4 ± 3 days) – Telephone Check-In (Section 6.20)

• Record concomitant medications and adverse events (Sections 6.4 and 6.5)

¹ Study drug may be administered at the study site after pre-dose PK samples have been collected.

8.5 Visit 4 (Week 8 ± 5 days) – Site Visit

- Collect Patient/Observer-reported scales (Section 6.11)
- Record concomitant medications and adverse events (Sections 6.4 and 6.5)
- Collect urine sample for urinalysis and pregnancy test, if applicable (Sections 6.15.1.3 and 6.15.1.4)
- 12-lead ECG and Holter monitoring (Section 6.6)
- Collect vital signs (Section 6.7)
- Symptom-directed physical exam (Section 6.8)
- Complete dermatologic examination (Section 6.12)
- Take digital photography (Section 6.13)
- Complete VIIS (Section 6.9)
- Complete clinician-reported global impression of severity scale (Section 6.10)
- PD sample collection (Section 6.14)
- Collect blood samples for hematology and chemistry (Sections 6.15.1.1 and 6.15.1.2)
- PK sample collection¹ (blood and urine) (Section 6.16)
- Apply study drug to all areas of ichthyosis (Section 5.6)
- Dispense and collect study drug supply and diary (Sections 6.18.1 and 6.18.2)

8.6 Visit 5 (Week 12 ± 3 days) – Telephone Check-In (Section 6.20)

• Record concomitant medications and adverse events (Sections 6.4 and 6.5)

8.7 Visit 6 (Week 16 ± 5 days) – Site Visit

- Collect Patient/Observer-reported scales (Section 6.11)
- Record concomitant medications and adverse events (Sections 6.4 and 6.5)
- Collect urine sample for urinalysis and pregnancy test, if applicable (Sections 6.15.1.3 and 6.15.1.4)
- Collect vital signs (Section 6.7)
- Symptom-directed physical exam (Section 6.8)
- Complete dermatologic examination (Section 6.12)
- Take digital photography (Section 6.13)
- Complete VIIS (Section 6.9)
- Complete clinician-reported global impression of severity scale (Section 6.10)

¹ Study drug may be administered at the study site after pre-dose PK samples have been collected.

- PD sample collection (Section 6.14)
- Collect blood samples for hematology and chemistry (Sections 6.15.1.1 and 6.15.1.2)
- PK sample collection¹¹ (blood only) (Section 6.16)
- Apply study drug to all areas of ichthyosis (Section 5.6)
- Dispense and collect study drug supply and diary (Sections 6.18.1 and 6.18.2)

8.8 Visit 7 (Week 20 ± 3 days) – Telephone Check-In (Section 6.20)

• Record concomitant medications and adverse events (Sections 6.4 and 6.5)

8.9 Visit 8 (Week 24 ± 5 days) – Early Termination – Site Visit

- Collect Patient/Observer-reported scales (Section 6.11)
- Record concomitant medications and adverse events (Sections 6.4 and 6.5)
- Collect urine sample for urinalysis and pregnancy test, if applicable (Sections 6.15.1.3 and 6.15.1.4)
- 12-lead ECG and Holter monitoring (Section 6.6)
- Collect vital signs (Section 6.7)
- Symptom-directed physical exam (Section 6.8)
- Complete dermatologic examination (Section 6.12)
- Take digital photography (Section 6.13)
- Complete VIIS (Section 6.9)
- Complete clinician-reported global impression of severity scale (Section 6.10)
- PD sample collection (Section 6.14)
- Collect blood samples for hematology and chemistry (Sections 6.15.1.1 and 6.15.1.2)
- PK sample collection (blood and urine) (Section 6.16)
- Collect study drug supply and diary (Sections 6.18.1 and 6.18.2)
- Conduct Subject Exit Interview¹ (Section 6.21)

8.10 Visit 9 (Week 28 ± 5 days) – Safety Follow-up – Site Visit

- Collect Patient/Observer-reported scales (Section 6.11)
- Record concomitant medications and adverse events (Sections 6.4 and 6.5)
- Complete dermatologic examination (Section 6.12)
- Take digital photography (Section 6.13)

¹ Subject Exit Interview should be conducted within 30 days of the scheduled visit.

- Complete VIIS (Section 6.9)
- Complete Global Impression of Severity (Section 6.10)

9 ADVERSE EVENT REPORTING

AEs will be collected from the time the subject signs the informed consent form through 30 days after the last study drug administration.

9.1.1 Adverse Event

An AE is any untoward medical occurrence in a patient or clinical investigation patient administered a study drug and which does not necessarily have a causal relationship with this treatment. An AE can therefore be any unfavorable and unintended sign (including an abnormal laboratory finding), symptom, or disease temporally associated with the use of the study drug, whether or not it is considered related to the study drug.

Abnormal laboratory and other abnormal investigational findings (i.e., physical exam) should not be reported as AEs unless they are associated with clinical signs and symptoms, lead to treatment discontinuation or are otherwise considered clinically relevant by the Investigator. In cases of surgical or diagnostic procedures, the condition/illness leading to such a procedure is considered as the AE rather than the procedure itself. In case of a fatality, the cause of death is considered as the AE, and the death is considered as its outcome.

9.1.1.1 Events Not to Be Considered as Adverse Events

Pre-existing medical conditions/signs/symptoms present before the Screening Visit that do not worsen in severity or frequency during the study are defined as baseline medical conditions, and are not to be considered AEs.

Pregnancies are not considered AEs but must be reported, see Section 9.1.8.

9.1.1.2 Recording Adverse Events

All AEs must be recorded in the site's study records and the AE CRF. Investigators should use correct medical terminology when recording events and avoid abbreviations.

The Investigator should attempt to establish a diagnosis of the AE based on signs, symptoms and/or other clinical information. The diagnosis, and not the individual signs/symptoms or laboratory abnormalities, should be documented in the subject's source documents and the CRF unless the etiology of the event is unknown. If signs/symptoms cannot be medically characterized as a single diagnosis or syndrome at the time of reporting, each individual event should be recorded as an AE. If a diagnosis is subsequently established, it should be reported as follow-up information.

An assessment should be made at each visit (or more frequently if necessary) of any changes in severity, the suspected relationship to study drug, the interventions required to treat it, and the outcome.

9.1.1.3 Assessment of Causality and Severity

For each AE recorded, the Investigator will make an assessment of causality and severity as follows:

- Relationship to Study Drug: The Investigator must assess whether they consider an AE to be drug-related. In assessing this relationship, the Investigator must use information about the drug as outlined in the Investigator's Brochure, the subject's pre-existent medical conditions/concurrent medication, and chronology of the event relative to drug administration. The following definitions will be used:
 - **Definitely or possibly related** applies to those AEs that, after careful medical consideration at the time they are evaluated, are considered by the Investigator (or other qualified physician) to have at least a possible relationship to study drug.
 - **Unlikely or not related** applies to those AEs that, after careful medical consideration at the time they are evaluated, are considered by the Investigator (or other qualified physician) to have no relationship, or an unlikely possibility of a relationship, to study drug.
- 2. Event Severity: The Investigator will be asked to use their medical judgment to assess the severity of the AE.

The following are guidelines to be used by the Investigator to judge the event severity of an AE:

- Mild awareness of sign or symptom, but easily tolerated
- Moderate discomfort enough to cause interference with usual activity
- Severe incapacitating with inability to work or perform usual activity
- Life-Threatening
- 3. Duration: Start and end dates and times, or if continuing.
- 4. Frequency: whether the event is a single episode, recurrent or continuous.
- 5. Action taken.
- 6. Whether it constitutes a SAE, per definition below.
- 7. Outcome: resolved, resolved with sequelae, continuing, death, or unknown (only for subjects that are lost to follow-up).

9.1.2 Treatment-Emergent Adverse Events

A TEAE will be an AE that occurred during the study after the first dose of study drug or that was present prior to dosing and exacerbates after the first dose of study drug.

9.1.3 Serious Adverse Events

An SAE is any AE that results in any of the following outcomes:

- Death: This includes death unrelated to the study drug (e.g., car accident). If some subject dies during the study and an autopsy is performed, autopsy results will become part of the subject's study chart and a copy should be sent to the Sponsor.
- Life-threatening experience: Life-threatening means that the patient was at immediate risk of death from the reaction as it occurred (i.e., it does not include a reaction which hypothetically might have caused death had it occurred in a more severe form).
- Required or prolonged inpatient hospitalization: Exceptions will be hospitalizations for a) elective or preplanned treatment for a pre-existing condition that is unrelated to the

indication under study and has not worsened since the start of study drug or b) treatment on an emergency outpatient basis for an event not fulfilling any of the definitions of a SAE and not resulting in hospital admission.

- Persistent or significant disability/incapacity.
- Congenital anomaly.
- Important medical events that may not result in death, be immediately life threatening, or require hospitalization may be considered a SAE when, based upon medical judgment, they may jeopardize the patient and may require intervention to prevent one of the outcomes listed above.

9.1.4 Unexpected Adverse Event

An unexpected adverse event is defined as an AE, the nature or severity of which is not consistent with the information in the Investigator's Brochure.

9.1.5 Reporting Serious Adverse Events

The Investigator is responsible for reporting all SAEs, regardless of causality, to the Sponsor designee within 24 hours of learning of the occurrence. SAEs should be sent to:

(Local toll-free numbers will be provided on the SAE report form cover sheet.)

The reporting timeframe starts when the subject signs the informed consent or assent form through 30 days after the last study drug administration. At a minimum, a description of the event and the Investigator's judgment of causality must be provided at the time of the initial report. These preliminary reports will be followed by detailed descriptions that will include copies of hospital case reports, autopsy reports, and other documents when requested and applicable.

A follow-up SAE Report must be submitted within 24 hours of the Investigator receiving the follow-up information (such as information regarding complications, progression or resolution).

An SAE that is considered completely unrelated to a previously reported event should be reported separately as a new SAE.

The procedures for reporting SAEs are as follows:

- Complete the "Serious Adverse Event Report Form." The Investigator may contact Pharmacovigilance via the telephone hotline for assistance with SAE reporting.
- Fax or email the SAE Form to the attention of Pharmacovigilance within 24 hours of the Investigator's knowledge of the event.

The original copy of the SAE Report Form and the fax confirmation sheet (or email) must be kept with the source documentation at the study site.

Follow-up information should be communicated the same way, using a new SAE Report Form stating that it is a follow-up to the previously reported SAE and giving the date of the original report. The follow-up information should describe whether the event has resolved or continues, if and how it was treated, and whether the subject continued or withdrew from study participation.

The Investigator and study personnel should institute any supplemental investigations of SAEs based on their clinical judgment of likely causative factors. This may include clinical laboratory

tests not specified in the protocol, histopathologic examinations, or consultations with specialists. The Sponsor or their designee may also request the Investigator to conduct supplemental assessments.

If the SAE was not previously documented in the Investigator's Brochure and is thought to be related to study drug, the Sponsor or their designee may urgently require further information from the Investigator for regulatory authority reporting. The Sponsor may need to issue an Investigator Notification to inform all Investigators involved in any study with the same drug that this SAE has been reported.

The Investigator should notify Pharmacovigilance of any death or SAE occurring after a subject has withdrawn from the study when such a death occurs within 30 days of the last dose of study drug and may reasonably be related to the study drug.

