3 INVESTIGATIONAL PLAN

3.1 Overall Study Design and Plan

This is a two-part, randomized, double-blind, vehicle-controlled, parallel-group Phase 3 clinical trial with an initial assessment of increasing BSA treatment (Part 1). After the completion of Part 1, a separate set of eligible subjects will be enrolled into Part 2.

Part 1 Design:

Part 1 will evaluate the safety, tolerability, and efficacy of treatment to the affected area of ichthyosis initially on approximately 20% BSA and then increasing up to 90% BSA over 24 weeks of exposure and will confirm an appropriate sample size for Part 2.

Subjects will be consented and screened for eligibility. Approximately 9 subjects will be randomized in a 2:1 ratio to receive ADX-102 1% or vehicle.

Subjects or caregivers will apply study drug (i.e., ADX-102 1% or vehicle) to a treatment area identified by the Investigator.

The initial treatment area will be defined as approximately 20% BSA with Grade 2 or higher on the VIIS scaling severity score, as assessed by the Investigator, and will include one of the body sites as defined in the VIIS tool (target efficacy area).¹ From Week 1 through Week 12, subjects will receive treatment once daily in the initial treatment area only.

If the Investigator determines that there are no safety or tolerability issues at the end of Week 12, the treatment area will increase to all of the affected areas of ichthyosis on one-half of the body (approximately 40-45% BSA in a typical SLS patient). From Week 13 through Week 20, subjects will receive treatment once daily on the expanded treatment area.

If there are still no safety or tolerability issues at the end of Week 20, the treatment area will further increase to all affected areas of ichthyosis on the entire body (approximately, 80-90% BSA in a typical SLS patient). Subjects will receive treatment once daily treatment on all affected areas from Week 21 through Week 24.

Subjects completing the 24 weeks of study drug treatment will then be monitored for an additional 4 weeks for safety.

Subjects who are randomized in Part 1 will not be eligible to participate in Part 2.

¹ Dorsal foot cannot be selected as the target efficacy area.

Part 2 Design:

Part 2 will evaluate the safety, tolerability, and efficacy of treatment to the affected area of ichthyosis on the body (approximately 80-90% BSA in a typical SLS patient) over 24 weeks of exposure.

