4.3 Subject Withdrawal and Replacement

Subjects and caregivers will be informed that they have the right to withdraw the subject from the study at any time for any reason, without prejudice to their medical care. The Investigator also has the right to withdraw subjects from the study for any of the following reasons:

- Progression of disease that, in the opinion of the Investigator, precludes further study drug treatment,
- Development of an unacceptable AE or SAE,
- Subject or Sponsor request,
- Subject non-adherence to study drug dosing or protocol requirements, or
- Pregnancy.

The reason for study withdrawal is to be documented in the subject's source documents and CRF. Withdrawn subjects may be replaced at the discretion of the Sponsor.

Subjects who prematurely discontinue from the study should be seen as soon as possible for Week 24 assessments (Part 1:Table ; Part 2:Table 2).

For subjects who are lost to follow-up (i.e., those subjects whose status is unclear because they fail to appear for study visits without stating an intention to withdraw), the Investigator should show due diligence by documenting in the source documents all steps taken to contact the subject (e.g., dates of telephone calls, registered letters, etc.).

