6.5 Adverse Events

AEs will be collected from the time the subject signs the informed consent form through 30 days after the last dose of study drug. AEs must be recorded in the subject's CRF. The Sponsor and Investigator or qualified study personnel will review and evaluate adverse events on an ongoing basis. See Section 9 for further detail on AE reporting.

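### Protocol 9.1.5 gives two inconsistent rules for serious events after withdrawal: every SAE regardless of causality, and a closing sentence conditioned on relatedness, within the same 30 days after last dose

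*Protocol*

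**What the plan says.** The general rule in Protocol 9.1.5 is: "The Investigator is responsible for reporting all SAEs, regardless of causality, to the Sponsor designee within 24 hours of learning of the occurrence". Its window is given in the same section: "The reporting timeframe starts when the subject signs the informed consent or assent form through 30 days after the last study drug administration". Neither sentence excludes subjects who have withdrawn.

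The last paragraph of 9.1.5 deals with withdrawn subjects separately. It says the Investigator should notify Pharmacovigilance of "any death or SAE occurring after a subject has withdrawn from the study", and then adds the condition "when such a death occurs within 30 days of the last dose of study drug and may reasonably be related to the study drug".

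Four other provisions bear on the point:

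- Section 6.5: "AEs will be collected from the time the subject signs the informed consent form through 30 days after the last dose of study drug".
- Section 9: "AEs will be collected from the time the subject signs the informed consent form through 30 days after the last study drug administration". Like 6.5, it has no causality condition.
- Section 9.1.3 counts deaths unrelated to study drug as SAEs.
- Section 9.1.7 has the Investigator report deaths from any cause to the IRB/REB/IEC.

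**The concern.** An investigator who learns of a serious event in a subject who has left the study will look for the rule on that situation. The paragraph that addresses it is narrower than the general rule. It brings in the investigator's opinion on causality as a condition for notification, which the general rule expressly excludes.

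At stake is the completeness of serious-event reporting in the 30 days after last dose. If two sites read the section differently, the same event is reported from one and not from the other. An SAE that never reaches the sponsor's safety function is hard to recover later. The efficacy analysis is not affected.

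**Working it through.** No arithmetic applies, and the plan has no figure to reproduce. The check is a comparison of the provisions.

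| Provision | Subjects | Events | End of window | Causality condition |
|---|---|---|---|---|
| 9.1.5, general rule | All, no exception for withdrawal | All SAEs | 30 days after last dose | None |
| 9.1.5, closing sentence | Withdrawn | Opens with deaths and SAEs; conditions refer to a death | 30 days after last dose | Reasonable possibility of relatedness |
| 6.5 and 9 | All, no exception for withdrawal | All AEs | 30 days after last dose | None |
| 9.1.7 (to IRB/REB/IEC) | No exception for withdrawal | Deaths | Not stated | None for deaths |

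**Window.** Both rules in 9.1.5 stop 30 days after last dose. The closing sentence therefore cannot be read as a late-reporting rule that adds to the general one. Within the shared window, the only difference it can make is to reduce what is notified.

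**Events arising after withdrawal and within 30 days of last dose:**

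1. Death, possibly related: reportable under both rules.
2. Death, judged unrelated: reportable under the general rule, outside the closing sentence.
3. Non-fatal SAE, possibly related: reportable under the general rule. The closing sentence is unclear, because it names SAEs at the start but attaches its conditions to deaths.
4. Non-fatal SAE, judged unrelated: reportable under the general rule. It is outside the closing sentence if the relatedness condition is taken to carry over to SAEs, and unclear otherwise.

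The rules agree in case 1, conflict in case 2, and cannot be matched with confidence in cases 3 and 4. The filter is explicit for deaths and at most implied for non-fatal SAEs.

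**Against the other sections.** Case 2 is an SAE by the definition in 9.1.3 and an AE to be collected under 6.5 and 9. Under 9.1.7 it goes to the IRB/REB/IEC. Read literally, the closing sentence would not require it to go to Pharmacovigilance. The relatedness wording in that sentence is also not one of the causality categories defined in 9.1.1.3, so a site has no stated way to map its assessment onto the condition.

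**Size.** The documents state no withdrawal rate and no SAE rate for this trial, so an expected number of affected events cannot be calculated.

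**The case against.** The strongest reply is that the general rule already gives the right answer. It covers all SAEs to day 30 without exception. The closing sentence says the Investigator should notify; it does not say that nothing else need be notified, and it does not override the general rule. Sections 6.5 and 9 collect every AE over the same period. This stands. It means under-reporting follows only if a site acts on the narrower sentence. A reader might infer that sites will fail to report; the documents support only that they may.

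Second, an event that leads to withdrawal occurs before withdrawal and is fully reportable under the general rule. The early leaver also has the early-termination visit: "Subjects who prematurely discontinue from the study should be seen as soon as possible for Week 24 assessments". This stands too. The exposed group is new events after withdrawal that are judged unrelated.

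Third, a reader might infer that early leavers have no safety follow-up, because Section 3.1 says of Part 1: "Subjects completing the 24 weeks of study drug treatment will then be monitored for an additional 4 weeks for safety". That is a separate question from the conflict in 9.1.5. Section 3.5 describes the 4-week follow-up for enrolled subjects generally. Requiring Visit 9 for early leavers would not settle the matter either. Visit 9 is nominally 28 days after Week 24, with a window of ±3 days in Part 1 and ±5 days in Part 2. Even for a completer whose last dose is at nominal Week 24, it can fall on day 28 − 3 = 25 or day 28 − 5 = 23, short of day 30.

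The reply does not remove the inconsistency. A section that needs the reader to ignore its most specific sentence in order to reach the intended result should be corrected, and nothing in the documents gives a reason for keeping the narrower condition.

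**Conclusion.** The inconsistency is real and confined to 9.1.5. Two rules cover the same 30 days; one has no causality filter and the other has one, and the second is unclear for non-fatal SAEs. The practical exposure is a new death or SAE, arising after withdrawal and within 30 days of last dose, judged unrelated, at a site that follows the closing sentence. This rests on the text alone and on the assumption that some site could read the specific sentence as governing. How often that would happen cannot be estimated.

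Three stronger readings are not supported:

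- **The safety data sent to the DSMB are biased low.** This would need evidence that sites apply the narrower sentence and that such events occur. The documents offer neither.
- **Subjects mostly stop early because of adverse events or laboratory findings.** The SAP (8.6 and 9.2.1) describes treatment interruptions due to laboratory findings, after which many subjects still received the full course. These are not withdrawals. The Phase 2 summary in Protocol 1.3.1 reports no SAEs and no TEAEs leading to discontinuation.
- **One missed SAE among the six active Part 1 subjects would shift incidence materially.** That is true of any single event in six subjects and says nothing about how likely a missed event is.

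**What to change.** Rewrite the last paragraph of Protocol 9.1.5 so that it matches the general rule. Delete the relatedness condition and the wording that ties the conditions to deaths. Suggested text:

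> All deaths and SAEs that occur within 30 days of the last dose, whatever the causality assessment, are reported to Pharmacovigilance within 24 hours of the Investigator learning of them. This includes events in subjects who have withdrawn.

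This brings the paragraph into line with Sections 6.5, 9 and 9.1.3. It also ensures that a death in that period that goes to the IRB/REB/IEC under 9.1.7 goes to Pharmacovigilance as well.

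The correction needs no added visit and no new rule for SAEs after day 30; either would be new policy rather than reconciliation. The cost is one paragraph in a protocol amendment and a note to sites. No procedure, data item or analysis changes.
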